10.1.9 Phone Visits

Phone visits -- Weeks 18, 30 and 44 -- will be conducted for all subjects to review any adverse event or concomitant medication changes.

Subjects will call the site when psoriasis returns prior to restarting application of study drug.

10.2 Efficacy Evaluations

10.2.1 Investigator's Global Assessment (IGA)

Investigator's Global Assessments ('whole body') will be performed at the following study visits. The IGA should be completed prior to other physician assessments.

Day 1, Weeks 4, 12, 24, 36, and 52

The IGA is a static evaluation of qualitative overall psoriasis severity. This global assessment scale is an ordinal scale with five severity grades (reported only in integers of 0 to 4). Each grade is defined by a distinct and clinically relevant morphologic description that minimizes inter-observer variability.

Unlike the Phase 2b study, an Intertriginous-IGA will not be done in this open-label extension study. However, study medication should be applied to intertriginous areas if affected.

Note: Palms and soles will be treated in this study with study medication, but will not be counted towards IGA or BSA assessments. The scalp is not treated and will not be counted towards any assessments.

- **Every effort should be made for the same Evaluator to complete the IGA for the subject at every study visit.**
- **IGA will be assessed at clinic visits prior to the subject applying Investigational Product at home.**

Investigator Global Assessment of Disease (IGA)

Scale	Grade	Description
0	Clear	
 • Plaque thickening = no elevation or thickening over normal skin • Scaling = no evidence of scaling • Erythema = none (no residual red coloration but post-inflammatory hyperpigmentation may be present)
1	Almost Clear	
 • Plaque thickening = none or possible thickening but difficult to ascertain there is a slight elevation above normal skin level • Scaling = none or residual surface drying and scaling • Erythema = light pink coloration
2	Mild	
 • Plaque thickening = slight but definite elevation • Scaling = fine scales partially or mostly covering the lesions • Erythema = light red coloration
3	Moderate	
 • Plaque thickening = moderate elevation with rounded or sloped edges • Scaling = most lesions at least partially covered • Erythema = definite red coloration
4	Severe	
 • Plaque thickening = marked or very marked elevation typically with hard or sharp edges • Scaling = non-tenacious or thick tenacious scale, covering most or all of lesions • Erythema = very bright red coloration; extreme red coloration; deep red coloration

- **The standard ‘whole body’ IGA shown above will be recorded for every subject in the study.**

For subjects with intertriginous area involvement of at least 'mild' severity by IGA (I-IGA \geq 2) at Day 1 (using the IGA scale shown above but evaluating intertriginous areas ONLY and NOT whole body involvement), an IGA for the intertriginous region alone (I-IGA) will be recorded at weeks 4, 12, 24, 36 and 52.

This 'intertriginous area IGA' (I-IGA) should be done AFTER the 'standard whole body IGA' (primary endpoint) in subjects who qualify.

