ARQ-151-202 Amendment 1 April 12, 2019	
 • Added protocol revision history section • Updated Sponsor address • Added I-IGA and mPASI to secondary endpoints throughout • Added Cohort 2 (non ARQ-151-201) subjects throughout • Added phone visits at Weeks 18, 30 and 44 and added instructions for the subject to call the site prior to restarting study medication • Added additional inclusion and exclusion criteria for Cohorts 1 and 2 • Updated exclusion criteria to exclude moderate to severe liver impairment (Child-Pugh B or C) • Added Screening visit for non-ARQ-151-201 subjects including the Screening C-SSRS • Added Table 2, Wash out period for Medications and Treatments for Cohort 2 • Added Appendix 1 Columbia-Suicide Severity Rating Scale (C-SSRS) Baseline/Screening Version • Updated Columbia-Suicide Severity Rating Scale (C-SSRS) Since Last Visit Version to Appendix 2 and updated National Institute of Allergy and Infectious Diseases, Division of Microbiology and Infectious Diseases (DMID) Toxicity Table for Use in Trials Enrolling Healthy Adults (2014) Modified to Appendix 3 • Editorial and administrative changes throughout the protocol to clarify language and formatting to improve readability.

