4 SYNOPSIS

Compound	ARQ-151 cream 0.3%
IND	135,681
Clinical Indication	Chronic Plaque Psoriasis
Study Phase and Type	
 Phase 2 (2b) 52 week, long-term safety study of ARQ-151 cream 0.3%
Study Objectives	To assess long-term safety in a multicenter, open-label, 52-week study in subjects treated with ARQ-151 cream 0.3% after completing a 12-week Phase 2b study (ARQ-151-201) Cohort 1 and non-ARQ-151-201 subjects (Cohort 2).
Study Endpoints	
Primary Endpoints
 
 Occurrence of treatment emergent AEs (TEAEs) Occurrence of Serious Adverse Events (SAEs) 
Secondary Endpoints
 
 Proportion (%) of subjects achieving an Investigator Global Assessment (IGA) of clear or almost clear, as observed at Week 12 and subsequent scheduled visits. Proportion (%) of subjects who achieve 'clear' IGA, I-IGA (if applicable) and mPASI (Modified Psoriasis Area Severity Index) score and stop treatment to all lesions, time to re-starting study drug (duration of response). Proportion (%) of applicable subjects with intertriginous area involvement, 'I-IGA' score of 'clear' or 'almost clear' at week 12 and subsequent visits. Proportion of subjects who achieve a 75% reduction in mPASI at Week 12 and subsequent scheduled visits as compared to baseline.
Summary of Study Design	Open-label, long-term safety study of ARQ-151 cream 0.3% in subjects with chronic plaque psoriasis involving up to 25% total BSA. Cohort 1 eligible subjects will enroll into the long-term safety study on the same day as the Week 12 visit for the previous study (ARQ-151-201). Cohort 2 eligible subjects will enroll on Day 1 of this study. Study medication will be applied by the qualifying subjects topically QD for 52 weeks at home. Periodic clinic visits will include assessments for clinical safety, application site reactions evaluated in the clinic using the method of Berger and Bowman, and disease improvement or progression.

Blinding	
 • This study is open label • All participants will receive ARQ-151 cream 0.3%
Countries:	United States and Canada
Number of sites	Approximately 30 sites
Study Population	Subjects who have completed the 12 week treatment period in study ARQ-151-201 and are willing to enroll in this 52-week extension study (Cohort 1) and qualified non-ARQ-151-201 subjects (Cohort 2).

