Efficacy Analysis	
The efficacy endpoints will be defined as:
 
 • Proportion (%) of subjects achieving an Investigator Global Assessment (IGA) of clear or almost clear, as observed at Week 12 and subsequent scheduled visits. • In subjects who achieve 'clear' IGA, I-IGA and MPASI scores and stop treatment to all lesions, time to re-starting study drug (duration of response) • Proportion (%) of applicable subjects with intertriginous area involvement, 'I-IGA' score of 'clear' or 'almost clear' at week 12 and subsequent visits • Proportion (%) of subjects achieving a 75% reduction from Baseline of Modified Psoriasis Area Severity Index-75 (mPASI-75) at weeks 12, 24, 36 and 52 as compared to Baseline.
Power and Sample Size	
Up to approximately 300 subjects are planned for Cohort 1 and up to approximately 100 subjects are planned for Cohort 2.
 
The sample size will provide a sufficient population size to evaluate the long-term safety of ARQ-151 cream 0.3% at 52 weeks.

Statistical Analysis:	
This study is not intended to assess efficacy, but rather the IGA, I-IGA and mPASI are included to determine the need for treatment and subsequent re-treatment after treatment course in Study ARQ-151-201 or Study ARQ-151-202. Certain efficacy data and endpoints will, however, be summarized.
 
Descriptive statistics will be presented for the endpoint data collected in the clinical trial. For analysis of the proportion (%) of subjects achieving an IGA of clear or almost clear at week 52, as observed, no imputation for missing data will be performed. The proportion of successes for the secondary variables of I-IGA and 75% reduction in mPASI will be tabulated.
 
The duration of response will be analyzed using the Kaplan-Meier method.
 
No formal inferential statistics will be performed on safety assessments. Descriptive statistics will be calculated for quantitative safety data and frequency counts will be compiled for classification of qualitative safety data.

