8.2 Study Endpoints

8.2.1 Primary Endpoint

The primary endpoint will be analysis of safety monitored through application site assessments in the clinic using the method of Berger and Bowman, clinical laboratory testing, 12-lead ECGs, PHQ-8, C-SSRS and adverse events. Two primary endpoint analyses are planned:

- Occurrence of Treatment Emergent Adverse Events
- Occurrence of Serious Adverse Events

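### Section 10.2.1 says the intertriginous IGA will not be done, yet the same section schedules it at five visits and two of four secondary endpoints use it

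*Protocol*

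**What the plan says.** Section 10.2.1 gives the instructions for rating disease severity. After introducing the whole-body scale it states: "Unlike the Phase 2b study, an Intertriginous-IGA will not be done in this open-label extension study". No exception is made for cohort or for subjects with intertriginous disease.

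After the scale table, the same section gives rules for that very assessment:

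- Who: "For subjects with intertriginous area involvement of at least 'mild' severity by IGA", meaning a score of 2 or more on Day 1, rated on intertriginous areas only.
- When: "an IGA for the intertriginous region alone (I-IGA) will be recorded at weeks 4, 12, 24, 36 and 52".
- Order: the I-IGA "should be done AFTER the 'standard whole body IGA' (primary endpoint) in subjects who qualify".

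Elsewhere I-IGA is treated as part of the study. The Synopsis lists among the secondary endpoints "Proportion (%) of subjects who achieve 'clear' IGA, I-IGA (if applicable) and mPASI", and its Efficacy Analysis row repeats the idea: "In subjects who achieve 'clear' IGA, I-IGA and MPASI scores and stop treatment to all lesions". Section 8.2.2 carries the same endpoint and a separate one for the proportion clear or almost clear on I-IGA from Week 12. The revision history for Amendment 1 records "Added I-IGA and mPASI to secondary endpoints throughout".

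**The concern.** One section tells the evaluator both to omit the rating and to perform it on a stated schedule. This is the section an evaluator would consult on how to rate, so a site could reasonably act on either instruction.

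Three things are at stake.

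- **The I-IGA endpoint.** Ratings not taken at a visit cannot be reconstructed, and Section 11.1 says missing efficacy data will not be estimated. The endpoint would rest only on sites that read past the first statement.
- **The denominator.** The endpoint applies to subjects who qualify on the Day 1 I-IGA. If a site does not take it for a Cohort 2 subject, nobody can later say whether that subject belonged in the endpoint, so the number of missing applicable subjects there is unknown as well.
- **The definition of clear.** Sections 10.5 and 10.8 include I-IGA, where applicable, in the confirmation of clearance from which duration of response starts. Sites could apply that definition with or without it.

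The wording on the order of ratings also labels whole-body IGA the primary endpoint, which Section 8.2.1 contradicts.

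**Working it through.** No sample size, power or error rate is involved, and the plan gives no figure to reproduce. The check is a comparison of places and a count.

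**1. Can the two statements be reconciled?** The first is unconditional. The second requires the rating in qualifying subjects at named visits. No subgroup or visit satisfies both.

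**2. Which is the outlier?** Places in the current text that rely on I-IGA:

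| Role | Where |
|---|---|
| Secondary endpoint | Synopsis (Study Endpoints, Efficacy Analysis); Section 8.2.2 |
| Scheduled assessment | Section 5 flow chart; Section 10.1, Day 1 Visit; Section 10.2.1, after the scale table |
| Part of the definition of clear | Synopsis; Sections 8.2.2, 10.5 and 10.8 |
| Tabulated variable | Synopsis (Statistical Analysis); Section 11.3 |

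Against these stands one sentence. The Synopsis and Section 11.3 add that I-IGA is included to inform decisions on treatment and re-treatment. The Amendment 1 entry suggests, without proving, that the sentence survived from before I-IGA was added. The contradiction does not depend on that entry, since both statements are current text.

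**3. Ratings lost per qualifying subject at a site that follows the first statement.**

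- Section 10.2.1 visits: Weeks 4, 12, 24, 36, 52 = 5, in either cohort.
- Of these, visits in the I-IGA endpoint (Week 12 onward): 12, 24, 36, 52 = 4.
- Flow chart row for Cohort 2: Screening + Day 1 + 5 = 7. Of the two extra ratings, Day 1 decides who qualifies; Screening feeds no stated endpoint.

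**4. Secondary endpoints in Section 8.2.2 that use I-IGA.** Whole-body IGA: no. Duration of response: yes. I-IGA clear or almost clear: yes. mPASI-75: no. That is 2 of 4.

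**5. Is the Day 1 rating lost in both cohorts?** For Cohort 1, Section 10.1 lists I-IGA among the assessments obtained at Week 12 of ARQ-151-201 and used as Day 1, so qualification should be known. The exception is any Cohort 1 subject who enters after completing ARQ-151-201 and goes through screening (footnote h in Section 5; Section 10.1). For Cohort 2 the rating would be taken in this study and would be lost.

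**6. How much does duration of response depend on I-IGA?** Section 10.8 defines clear as whole-body IGA 0, I-IGA 0 where applicable, and mPASI 0. Whole-body IGA 0 already excludes thickening, scaling and erythema, and mPASI 0 means no disease. A subject meeting both should rarely fail on I-IGA.

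**7. The label.** Section 8.2.1 says "Two primary endpoint analyses are planned" and names treatment-emergent adverse events and serious adverse events. Section 8.2.2 places IGA among the secondary endpoints. The label in Section 10.2.1 is wrong.

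**The case against.** The best case on the other side is about weight. A site that reads Section 10.2.1 to its end finds explicit rules on who, when and in what order, and the flow chart marks I-IGA at every clinic visit. Harm requires a site to prefer one sentence over all of that, and nothing shows how many would. The protocol says the study is not intended to assess efficacy, and the endpoints concerned are descriptive. This stands and limits the severity. It does not remove the contradiction.

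Counting two affected endpoints may also overstate the effect, since I-IGA is nearly redundant in the definition of clear. That is fair: the I-IGA proportion is the endpoint materially exposed.

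Body diagrams could bound the number of Cohort 2 subjects with intertriginous involvement. They could give an upper limit, but they do not supply the regional severity grade of 2 or more on which qualification depends.

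That Cohort 1 qualification is known rests on data from ARQ-151-201, which cannot be inspected here. Section 10.1 does say the rating is obtained there, but late Cohort 1 entrants remain an exception.

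Finally, deleting only the one sentence would leave the next one opening with a contrast to nothing. That is correct and is dealt with in the fix.

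An SAP would not cure the problem. It can define how ratings are analysed, but it does not instruct sites to take a rating the protocol says is omitted.

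**Conclusion.** The concern holds. Section 10.2.1 contradicts itself on whether I-IGA is performed, and the statement that it is not is the outlier. At a site that follows it, each qualifying subject loses 5 post-Day 1 ratings, 4 of them endpoint ratings; in Cohort 2 the Day 1 rating that fixes the denominator goes too. One secondary endpoint is directly exposed, and a second, duration of response, only slightly. The primary safety endpoints are unaffected, and no test or sample size depends on this.

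The per-subject counts assume full attendance at the scheduled visits. No total loss is claimed, because the protocol gives neither the number of qualifying subjects nor any way to tell which sites would follow which instruction. It should be fixed because the loss would be irrecoverable and the correction is nearly free. The primary-endpoint label is a separate, minor slip.

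**What to change.** In Section 10.2.1:

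1. Delete the sentence saying the intertriginous IGA will not be done.
2. Drop the opening contrast word from the following sentence, leaving its instruction on applying study medication unchanged.
3. Remove the words in parentheses that label whole-body IGA the primary endpoint.

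Optionally, where Section 10.2.1 defines who qualifies for I-IGA, spell out Day 1 as Sections 9.2 and 10.1 already define it: Week 12 of ARQ-151-201 for Cohort 1 and Day 1 of this study for Cohort 2. For Cohort 1 that is not the efficacy baseline visit, so a reader could take the wrong one.

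These edits bring Section 10.2.1 into line with Sections 10.5 and 10.8. They do not alter who qualifies for the rating, the clearance rule in Section 10.8, or any treatment instruction. The cost is a small text amendment and a note to sites. No visit or assessment is added, because the flow chart already includes I-IGA at every clinic visit. Ratings already missed under the deleted sentence could not be recovered; any site that omitted them should be identified, so that the I-IGA table can report how many subjects are affected.

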8.2.2 Secondary Endpoints

The secondary endpoints are related to efficacy and will include:

- Proportion (%) of subjects achieving an Investigator Global Assessment (IGA) of clear or almost clear, as observed at Week 12 and subsequent scheduled visits.
- In subjects who achieve 'clear' scores for IGA, I-IGA (if applicable **and** mPASI (Modified Psoriasis Area Severity Index) and stop treatment to all lesions, time to re-starting study drug (duration of response).
- Proportion (%) of applicable subjects with intertriginous area involvement, 'I-IGA' score of 'clear' or 'almost clear' at week 12 and subsequent visits
- Proportion (%) of subjects achieving a 75% reduction from Baseline of Modified Psoriasis Area Severity Index-75 (mPASI-75) at weeks 12, 24, 36 and 52 as compared to Baseline.

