9.2 Subject Participation

Subject participation involves a minimum of five clinic visits at Week 4, Week 12, Week 24, Week 36 and Week 52 of treatment. There will be three phone visits conducted at Weeks 18, 30 and 44. The Day 1 visit of this study will be Week 12 of the ARQ-151-201 study (Cohort 1) and Day 1 for Cohort 2. The Baseline values for Safety tabulations will be taken from the day that the subject received their first active study drug. Baseline values for efficacy will be those recorded on Day 1 of Study ARQ-151-201. The anticipated maximum duration of subject participation is about 52 weeks. Subjects in the ARQ-151-201 study that choose to participate in the long-term extension study will transition directly into the ARQ-151-202 study at the Day 1 visit (Week 12 of Study ARQ-151-201).

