At Day 1 (Week 12 of the ARQ-151-201 study or Day 1 for non ARQ-151-201) ARQ-151-201 subjects will be provided details of study requirements and sign an informed consent. Medical history and demographic data, psoriatic plaque assessments (IGA, I-IGA, mPASI and BSA), physical examination, vital sign measurements (blood pressure, heart rate, and temperature), PHQ-8, C-SSRS, laboratory tests: hematology, chemistry, urinalysis and a pregnancy test for female subjects of child bearing potential will be obtained at Week 12 visit of study ARQ-151-201 and will serve as the Day 1 for ARQ-151-201 subjects (Cohort 1). Cohort 2 Day 1 assessments for this long-term safety study (ARQ-151-202) will be completed within 35 days of Screening. The Baseline values for Safety tabulations will be taken from the day that the subject received their first active study drug (across studies ARQ-151-201 and ARQ-151-202). Baseline values for efficacy will be those recorded on Day 1 of Study ARQ-151-201 (Cohort 1) and Day 1 of ARQ-151-202 for non ARQ-151-201 subjects (Cohort 2).

Cohort 2 subjects must meet the required wash out period for any excluded medications and treatments according to [Table 2](#).

All Cohort 1 subjects will retain their Subject ID from the previous study which will be entered into the electronic subject tracking system for this long-term safety study. Cohort 2 subject study numbers will include the 2 digit site number and the three digit subject number will begin with 500.

Scheduled Visits (Day 1 and Visits 1 – 5)

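### Scheduled I-IGA follow-up depends on a score of 2 or more at this study's Day 1, so among active rollovers the I-IGA endpoint covers only those not yet clear or almost clear at entry

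*Protocol*

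**What the plan says.** - **Who is rated.** Protocol Section 10.2.1 takes subjects whose intertriginous disease is at least mild (I-IGA of 2 or more) "at Day 1 (using the IGA scale shown above but evaluating intertriginous areas ONLY and NOT whole body involvement". For them "an IGA for the intertriginous region alone (I-IGA) will be recorded at weeks 4, 12, 24, 36 and 52". It then repeats that the rating is done "in subjects who qualify".
- **What Day 1 means.** Section 9.2: "The Day 1 visit of this study will be Week 12 of the ARQ-151-201 study (Cohort 1) and Day 1 for Cohort 2". Section 10.1 lists the "psoriatic plaque assessments (IGA, I-IGA, mPASI and BSA" among the data taken at Week 12 of ARQ-151-201 to serve as Day 1 for Cohort 1.
- **The endpoint.** Section 8.2.2: "Proportion (%) of applicable subjects with intertriginous area involvement" who score clear or almost clear, from Week 12 onwards.
- **The efficacy baseline.** Section 9.2: "Baseline values for efficacy will be those recorded on Day 1 of Study ARQ-151-201". Section 10.1 splits this by cohort: "Baseline values for efficacy will be those recorded on Day 1 of Study ARQ-151-201 (Cohort 1) and Day 1 of ARQ-151-202" for Cohort 2.
- **Two other statements on I-IGA.** An earlier paragraph of Section 10.2.1 says that, unlike in the Phase 2b study, no I-IGA is performed in this extension. The Section 5 flow chart marks I-IGA at Screening, Day 1 and every clinic visit, with no minimum score.

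**The concern.** For Cohort 1 the qualifying score is taken after 12 weeks of treatment in the parent study. In subjects who received either active strength there (active rollovers), the rule therefore selects on an outcome of treatment: a subject whose intertriginous plaques responded does not qualify, and one whose plaques did not respond does. Cohort 2 and vehicle rollovers are selected on a score that precedes their first active dose. One proportion would then combine groups with different meanings.

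A 52-week extension is also where one would look to see whether an intertriginous response lasts. Under this rule, the subjects who had such a response at entry are the ones without scheduled grades. The rule governs data collection, so no analysis plan can repair it afterwards.

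**Working it through.** The plan gives no figure to reproduce, so the check is mainly one of definitions.

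**Step 1: which Day 1.** Section 10.2.1 names no study. Where the protocol means the parent study's first day, it says so (Section 5 footnotes, Sections 9.2, 10.1 and 11.1.1). The Weeks 4 to 52 that follow can only be on this study's clock, because ARQ-151-201 lasts 12 weeks. The natural reading is Day 1 of ARQ-151-202, which for Cohort 1 is Week 12 of ARQ-151-201.

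**Step 2: rule against endpoint.** To qualify, I-IGA must be 2 or more. Success is I-IGA of 0 or 1. The two sets do not overlap.

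| Group | When the qualifying score is taken | Success at entry among those who qualify |
|---|---|---|
| Active rollovers | after 12 weeks of active cream | 0%, by definition |
| Vehicle rollovers | before any active cream | 0%, by definition |
| Cohort 2 | before any active cream | 0%, by definition |

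The last column is the same for all three groups, but only in the first row does the rule remove people who had already responded to active drug. All active rollovers at 0 or 1 at Week 12 of the parent study are without scheduled I-IGA ratings at Weeks 4 to 52.

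**Step 3: distance from the baseline.** The Cohort 1 efficacy baseline is Day 1 of ARQ-151-201 and the I-IGA qualifying visit is 12 weeks later. Whole-body IGA is recorded in every subject and mPASI has no minimum score, so I-IGA is the only one of the three restricted in this way.

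**Step 4: can a bias be sized?** Among active rollovers with I-IGA of 2 or more at the ARQ-151-201 baseline, let p be the share at 0 or 1 by its Week 12, m their success rate at a later visit, and q the later success rate of the rest.

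- Rate in all of them: p × m + (1 − p) × q
- Rate under the rule: q
- Difference (rule minus all): p × (q − m)

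The protocol gives none of p, m or q. The values below are assumptions.

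| p | m | q | All | Under the rule | Difference |
|---|---|---|---|---|---|
| 0.3 | 0.6 | 0.4 | 0.18 + 0.28 = 0.46 | 0.40 | −6 points |
| 0.5 | 0.8 | 0.4 | 0.40 + 0.20 = 0.60 | 0.40 | −20 points |
| 0.7 | 0.8 | 0.2 | 0.56 + 0.06 = 0.62 | 0.20 | −42 points |
| 0.6 | 0 | 0.4 | 0 + 0.16 = 0.16 | 0.40 | +24 points |

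Over p of 0.3 to 0.7, m of 0.6 to 0.8 and q of 0.2 to 0.4, the rule understates by 6 to 42 points. If early responders lose their response (last row), the sign reverses. The sign is that of q − m, which is unknown. Only the omission of the share p follows from the text.

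**The case against.** The strongest reply is that the rule is not settled. The protocol gives three incompatible instructions: no I-IGA at all, I-IGA above a minimum score, and I-IGA for everyone at each clinic visit. Under the flow chart the early responders would be rated. Section 10.2.1 also calls the whole-body IGA the primary endpoint, although Section 8.2.1 names treatment-emergent and serious adverse events, which suggests text carried over from another protocol. This stands. The point applies to Section 10.2.1 as written, and the contradiction has to be resolved with it.

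Four stronger readings might be inferred. The protocol does not support them.

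- **That these subjects are never scored.** They have an I-IGA at Day 1, and Sections 10.5 and 10.8 call for one, where applicable, when clearance is confirmed. What is lost is the scheduled series from Week 4 to Week 52.
- **That intertriginous relapse would go unseen.** Whole-body IGA, mPASI, BSA and the body diagram continue, and a psoriasis flare is an adverse event. What is missing is a separate intertriginous grade.
- **That those who qualify are all treatment failures.** A fall from 4 to 2, or intertriginous disease new since the parent baseline, also qualifies.
- **That the rule contradicts the baseline definition.** I-IGA of 0 or 1 is a static score and needs no baseline value. The two visits differ, which harms interpretation, but the statements can coexist.

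Finally, Section 11.3 says the study is not intended to assess efficacy, and Section 10.5 leaves the tallying of categorical responses to the analysis plan. That lowers the severity. It does not recover ratings that were not taken.

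**Conclusion.** The concern holds for Section 10.2.1 as written, on the reading that its Day 1 is this study's Day 1. Active rollovers with intertriginous disease at the ARQ-151-201 baseline who were at 0 or 1 by Week 12 have no scheduled I-IGA afterwards. The endpoint in active rollovers is restricted to those not at 0 or 1 at entry, and it is not comparable with Cohort 2 or vehicle rollovers. Maintenance or loss of an intertriginous response is not graded in early responders.

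Neither the size nor the direction of a bias is established. The illustrative figures concern active rollovers only. The effect on a pooled proportion also depends on the mix of groups with intertriginous disease, which the protocol does not give.

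Severity is moderate: one descriptive secondary proportion in a subset is affected, and the primary safety analysis is not. Doing nothing would leave sites with three conflicting instructions on whether to rate at all.

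**What to change.** Amend Sections 5, 8.2.2 and 10.2.1 together:

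1. Delete the Section 10.2.1 statement that I-IGA is not performed in this study.
2. Record I-IGA at every scheduled clinic visit in all subjects with a score of 2 or more **either** at the efficacy baseline (Day 1 of ARQ-151-201 for Cohort 1, Day 1 of ARQ-151-202 for Cohort 2) **or** at Day 1 of this study. The second condition keeps subjects whose intertriginous disease first reached 2 by Week 12 of the parent study, whom a rule based on the parent baseline alone would drop.
3. Add the same condition as a footnote to the I-IGA entry in the flow chart.
4. Use the efficacy-baseline set as the denominator of the I-IGA endpoint, reported by cohort and by prior treatment (active or vehicle). The split matters because this set includes vehicle rollovers who may have cleared before any active drug. Summarise subjects who qualify only at this study's Day 1 separately.

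Name the qualifying visits outright in the amended text. Section 11.1.1 exempts only IGA, without mentioning I-IGA, from the later baseline it gives vehicle rollovers.

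The cost is a few sentences in an amendment and a short extra rating in some Cohort 1 subjects at visits that already take place.
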